2.5 Safety Analysis

The following variables will be evaluated for safety purposes:

- AEs and SAEs.
- Vital signs, including BP and heart rate.
- Local tolerability, including:
 - Subjective injection site discomfort as reported by subjects using age-appropriate discomfort scales.
 - Erythema and/or edema formation at site of injection assessed using the Draize scale.

2.5.1 Adverse events

All AEs will be coded by the Data Coordinating Center (The Emmes Corporation) using the Medical Dictionary for Regulatory Activities (MedDRA) and summarized by system organ class and preferred term, as well as by treatment dose. Number and percentage of subjects experiencing at least one AE after the G-Pen™ was administrated will be presented (Table 12). In addition, the severity of AEs post-dosing and their relatedness to study drug, device, and procedure will be assessed (Tables 13). Treatment emergent adverse event (TEAE), defined by AE occurring after administration of G-Pen™, and non-TEAE, defined by any AE that occurred after signing informed consent, will be presented in Tables 12 and 13.

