
Data management and statistical analysis:
	
Data will be entered from the source (e.g Case Report Forms) into Advantage eClinical an Electronic Database Capture (EDC) system by site personnel. Data will be monitored remotely and at on-site visits by the Clinical Research Associate (CRA).
 
Both primary and secondary endpoints will be summarized descriptively within each of the 3 age groups. Mean, standard deviation, median, minimum and maximum will be presented for continuous variables. Count and percentage variables will be presented for discrete variables. The primary endpoint will also be compared to 0 change using a simple t-test.
 
Pharmacokinetic data will be analyzed descriptively by dose/age cohort.

Sample Size Determination:
	
Based on results of a prior study, G-Pen™ (glucagon injection) is expected to increase glucose by minimally 25 mg/dL from baseline within 30 minutes of administration in every subject. Assuming a standard deviation of 18 mg/dL, a

sample size of 6 subjects per cohort has been chosen to provide 90% power to detect an increase of plasma glucose from baseline to 30 minutes after treatment.

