## 12. SAFETY AND ADVERSE EVENT (AE) REPORTING

### 12.1. Definition of an Adverse Event

An AE is any untoward medical occurrence in a clinical investigation subject administered a pharmaceutical product and which is not necessarily required to have a causal relationship with this treatment. An AE can therefore be any unfavorable and unintended sign, symptom, or disease temporally associated with the use of a medicinal product, whether or not considered related to the medicinal product. Examples of AEs include:

- Abnormal test findings
- Clinically significant symptoms and signs
- Changes in physical examination findings which are untoward and deemed clinically significant by the investigator.
- Allergy/hypersensitivity

The criteria for determining whether an abnormal objective test finding may be reported as an AE are as follows:

- Test result is associated with accompanying symptoms,
- Test result requires additional diagnostic testing or medical/surgical intervention,
- Test result leads to a change in study dosing or discontinuation from the study, significant additional concomitant drug treatment or other treatment, or
- Test result is considered to be an AE by the investigator or Sponsor.

Repeat of a test based on an abnormal result in the absence of the above conditions does not constitute an AE. Any abnormal test result determined to be an error does not require reporting as an AE.

A treatment-emergent AE (TEAE) is an AE that either commenced following initiation of study treatment or was present prior to study treatment but increased in frequency or severity following initiation of study treatment.

Standard medical terminology should be used in describing AEs. Informal descriptions should be avoided.

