1.1.2 Secondary Objectives

The secondary objectives of this study are:

- Evaluate the pharmacodynamics (PD) of G-Pen™. Additionally, in the 12.0-<18.0 year-old age group, to independently assess the plasma glucose change from baseline to 30 minutes after administration of G-Pen™ at a dose of 0.5 mg.
- Determine the safety and tolerability of G-Pen™ for each age group.
- Evaluate the pharmacokinetics (PK) of G-Pen™. The PK analysis will be performed by another organization, IMD (See Appendix II).

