1.2.2 Secondary Endpoints

The secondary endpoints for this study are as follows:

- PK parameters, including: descriptive analysis of serum glucagon AUC_{0-180m} , C_{max} and T_{max} of the different age group and overall population. These analyses will be conducted by IMD (See Appendix II).
- PD characteristics, including: descriptive analysis of plasma glucose AUC_{0-90m} , C_{max} , T_{max} and time to achieve an increase in plasma glucose of at least 25 mg/dL for each age group. In addition, in the 12.0-<18.0 year-old age group, plasma glucose change from baseline to 30 minutes after administration of G-Pen™ at a dose of 0.5 mg will be evaluated.
- Safety-related endpoints including:
 - Vital signs, including blood pressure (BP) and heart rate.
 - Incidence of adverse events (AEs) and serious adverse events (SAEs).
 - Subjective injection site discomfort assessed using the Faces Pain Scale (FPS-R).
 - Subjects with sufficient comprehension will further describe the nature and duration of any injection site discomfort using a second questionnaire.
 - Erythema and/or edema formation at site of injection assessed by an investigator using the modified Draize Scale.

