2 ANALYSIS PLAN

All endpoints will be analyzed descriptively within each of the three age groups. N (non-missing sample size), mean, standard deviation, median, minimum, and maximum will be presented for continuous variables. Count and percentage (based on the non-missing sample size) will be presented for discrete variables.

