		[Min-Max]	[xxx-xxx]	[xx-xx]	[xxx-xxx]	[xxx-xxx]	[xx-xx]
12.0-<18.0 years	1.0 mg	N	x	x	x	x	x
		Mean (SD)	xxx.x (xxx.x)	xx.x (xx.x)	xxx.x (xxx.x)	xxx.x (xxx.x)	xx.x (xx.x)
		Median	xxx	xx	xxx	xxx	xx
		[Min-Max]	[xxx-xxx]	[xx-xx]	[xxx-xxx]	[xxx-xxx]	[xx-xx]

AUC= area under the curve; C_{max}= maximum plasma concentration; T_{max}= time to maximum plasma concentration; SD= standard deviation.

Table 10: Plasma glucose AUC_{0-90m}, C_{max}, T_{max}, and time to increase by ≥ 25 mg/dL from baseline by treatment dose for subjects aged 12.0-<18.0

G-Pen™ Dose	Summary Statistics	C _{max} (mg/dL)	T _{max} (min)	AUC _{0-90m} (min*mg/dL)	Baseline-adjusted AUC _{0-90m} (min*mg/dL)	Time to increase by ≥ 25 mg/dL from baseline
1.0 mg	N	x	x	x	x	x
	Mean (SD)	xxx.x (xxx.x)	xx.x (xx.x)	xxx.x (xxx.x)	xxx.x (xxx.x)	xx.x (xx.x)
	Median	xxx	xx	xxx	xxx	xx
	[Min-Max]	[xxx-xxx]	[xx-xx]	[xxx-xxx]	[xxx-xxx]	[xx-xx]
0.5 mg	N	x	x	x	x	x
	Mean (SD)	xxx.x (xxx.x)	xx.x (xx.x)	xxx.x (xxx.x)	xxx.x (xxx.x)	xx.x (xx.x)
	Median	xxx	xx	xxx	xxx	xx
	[Min-Max]	[xxx-xxx]	[xx-xx]	[xxx-xxx]	[xxx-xxx]	[xx-xx]

AUC= area under the curve; C_{max}= maximum plasma concentration; T_{max}= time to maximum plasma concentration; SD= standard deviation.

[figure not shown]
Figure 2: Plasma glucose over time by age group

[figure not shown]
Figure 3: Plasma glucose over time by treatment dose for subjects aged 12.0-<18.0

Table 11: Plasma glucose over time by age group and by treatment dose for subjects aged 12.0-<18.0

Plasma Glucose, mg/dL Mean (SD)		Time (min)																			
Age Group	G-Pen™ Dose	-5	0	5	10	15	20	25	30	35	40	45	50	55	60	65	70	75	80	85	90
2.0-<6.0 years (N=X)	0.5 mg	xx.x (xx.x)	xx.x (xx.x)	xxx.x (xxx.x)																	
6.0-<12.0 years (N=X)	0.5 mg	xx.x (xx.x)	xx.x (xx.x)	xxx.x (xxx.x)																	
12.0-<18.0 years (N=X)	1.0 mg	xx.x (xx.x)	xx.x (xx.x)	xxx.x (xxx.x)																	
12.0-<18.0 years (N=X)	0.5 mg	xx.x (xx.x)	xx.x (xx.x)	xxx.x (xxx.x)																	

SD= standard deviation.

Safety Data

Table 12: Number and percentage of subjects experiencing adverse events by MedDRA® system organ class and preferred term, and treatment dose						
Non-treatment emergent adverse events (non-TEAE)						
MedDRA® System Organ Class (SOC)	MedDRA® Preferred Term (PT)	G-Pen™ Dose				
		0.5 mg (N=X)		1.0 mg (N=X)		
		n	%	n	%	
Any SOC	Any PT	xx	x.x	x	x.x	
[SOC 1]	Any PT	xx	x.x	x	x.x	
	[PT 1]	xx	x.x	x	x.x	
	[PT 2]	xx	x.x	x	x.x	
[SOC 2]	Any PT	xx	x.x	x	x.x	
	[PT 1]	xx	x.x	x	x.x	

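### Adverse events are tabulated by dose only, so incidence at 0.5 mg cannot be read by age group, and the SAP's TEAE and non-TEAE definitions depart from the protocol

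*SAP*

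**What the plan says.** **Commitment to age groups.** SAP section 2 opens with a general rule: "All endpoints will be analyzed descriptively within each of the three age groups". The protocol synopsis says likewise: "Both primary and secondary endpoints will be summarized descriptively within each of the 3 age groups". SAP 1.2.2 and Protocol 5.3.2 both list the incidence of AEs and SAEs as a secondary endpoint. The matching objective in SAP 1.1.2 is "Determine the safety and tolerability of G-Pen™ for each age group", and Protocol 5.2 agrees.

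**What is planned for AEs.** SAP 2.5.1 has them "summarized by system organ class and preferred term, as well as by treatment dose". The Table 12 shell in SAP Appendix I is titled "Number and percentage of subjects experiencing adverse events by MedDRA® system organ class and preferred term, and treatment dose". The shells of Tables 12 and 13 have two dose columns, 0.5 mg and 1.0 mg, and no age split. SAEs go into a footnote to the same tables. Protocol 13.3.1 names no age split either.

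**Definitions.** Under Protocol 12.1 a TEAE is an AE that starts after study treatment begins, or one that "was present prior to study treatment but increased in frequency or severity following initiation of study treatment". SAP 2.5.1 keeps only AEs occurring after G-Pen administration, and sets beside them "non-TEAE, defined by any AE that occurred after signing informed consent".

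**The concern.** The AE tables do not carry out the SAP's own general rule, and nothing in the SAP exempts AEs from it. Vital signs (SAP 2.5.3) and local tolerability (SAP 2.5.4) do follow it, by age group and by dose within ages 12-<18, so the AE tables look like an oversight.

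The 0.5 mg column is a mixture. For ages 2-<6 and 6-<12 it is the only dose. For ages 12-<18 it is a second exposure, 7-28 days after 1.0 mg. An event concentrated in the youngest children would be diluted, and a column without events would look like stronger reassurance for each age group than that group's own numbers give.

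The definitions raise a smaller, separate problem. The same event can be a TEAE under the protocol and not under the SAP, and the SAP's two categories overlap as worded.

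**Working it through.** The plan states no figure on this point, so there is none to reproduce.

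**Inputs**
- Protocol synopsis, Sample size: about 24 dosed, up to 8 per cohort, with a target of 6 evaluable per cohort.
- SAP 1.3: 36 dosed, up to 12 per group, with the same target of 6.
- SAP 1.1: ages 2-<12 receive 0.5 mg once; ages 12-<18 receive 1.0 mg, then 0.5 mg at visit 2.
- Protocol 13.3.1 and 10.3: percentages are of exposed subjects, and one dose is enough to enter the safety analysis.

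**Step 1. Who is in each column.** Take *n* subjects per age group, of whom *r* aged 12-<18 return for visit 2. The 0.5 mg column holds *n* + *n* + *r*; the 1.0 mg column holds *n*, all aged 12-<18. With everyone returning (*r* = *n*):

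| n per group | 0.5 mg column | 1.0 mg column |
|---|---|---|
| 6 | 18 | 6 |
| 8 | 24 | 8 |
| 12 | 36 | 12 |

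The 1.0 mg column can therefore be read by age; the 0.5 mg column cannot.

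**Step 2. What a pooled rate can hide.** A displayed *k*/(3*n*) is compatible with any rate from 0 to *k*/*n* in a given age group (for *k* ≤ *n*). The results 3/18, 4/24 and 6/36 all display as 16.7%. Each fits a rate in one age group anywhere from 0% to 50% (3/6, 4/8, 6/12).

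**Step 3. Four affected subjects, all aged 2-<6 (assumed).**
- Protocol maximum: 4/8 = 50.0%, shown as 4/24 = 16.7%.
- SAP maximum: 4/12 = 33.3%, shown as 4/36 = 11.1%.
- Protocol maximum with no visit 2 returns: shown as 4/16 = 25.0%.

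**Step 4. No events.** The one-sided 95% upper limit is 1 − 0.05^(1/*n*), where *n* is now the number of subjects with no events.
- Protocol sizes: 11.7% for 0/24, against 31.2% for 0/8.
- SAP sizes: 8.0% for 0/36, against 22.1% for 0/12.

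**Step 5. Other outputs.** Listings 1 to 3 cover protocol deviations, physical examination and pregnancies. None lists AEs.

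**Step 6. The definitions side by side.**

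| Event | Protocol 12.1 | SAP 2.5.1, read literally |
|---|---|---|
| Starts after dosing | TEAE | TEAE, and also non-TEAE because it follows consent |
| Starts between consent and dosing, does not worsen | Not a TEAE | Non-TEAE |
| Starts between consent and dosing, worsens after dosing | TEAE | Non-TEAE, if kept as one record with its first onset |

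Protocol 12.3 starts AE reporting at consent, so every reported TEAE falls inside the SAP's non-TEAE wording. In the third row the event is misclassified, not lost.

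**The case against.** The strongest reply is that this is a mismatch between a shell and a general rule, with little lost.

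- *Some safety data are split by age.* Table 3 gives withdrawals for AEs and deaths by age group. Protocol 12.2 does not count injection site reactions as AEs unless they need medical intervention, so most local events fall in the tolerability tables, which are split. This narrows the gap. But Table 3 gives reasons for discontinuation, not AE incidence, and non-local AEs are summarised only in Tables 12 and 13.
- *Safety results are listed for the sponsor (SAP 3.4), and the SAE footnote could state age.* SAP 3.4 describes ongoing review, not a report output. The footnote's content is unspecified, so age might appear there, but nothing requires it.
- *Zero events lose no information.* This is correct: a pooled zero means zero in each group, and the stratum sizes appear in other tables. The plan calls for no confidence limits. Step 4 shows only how much reassurance each denominator can support.
- *The example is a worst case.* It is. Four events in one group, at maximum enrolment, is an assumption and not a forecast.
- *Dose is the split closest to Protocol 13.3.1, and no inference depends on these tables.* Both are true, which limits the weight of the point. Neither meets the objective set for each age group.
- *The TEAE conflict is thin.* Only the SAP has TEAE panels, and those panels suggest that exclusive categories were intended. If a worsening is recorded as a new AE, it meets the SAP definition. Neither document says that it is, so classification depends on recording practice.

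**Conclusion.** The concern holds. Followed as written, the plan gives no AE or SAE incidence for ages 2-<6, 6-<12, or 12-<18 at 0.5 mg, so part of a stated secondary objective goes unanswered. At full return for visit 2, each age group supplies one third of the 0.5 mg column, and an event confined to one group appears at a third of its rate there. With no visit 2 returns, an event confined to either younger group appears at half its rate. These sizes assume equal groups; the event counts are illustrative.

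The effect is limited to AE reporting. The primary analysis, vital signs and local tolerability are untouched, and the 1.0 mg column is readable by age. The TEAE and non-TEAE wording is a lesser fault of the same section. The sponsor should correct both before the tables are produced.

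**What to change.** 1. In SAP 2.5.1 and the TEAE panels of Tables 12 and 13, replace the two dose columns with four strata: 2-<6 at 0.5 mg, 6-<12 at 0.5 mg, 12-<18 at 1.0 mg, and 12-<18 at 0.5 mg. Table 11 and the tolerability shells already use these. The TEAE panel of Table 13 is headed Table 14 (continued) in Appendix I, so correct that number too.
2. Present SAEs by the same strata.
3. Adopt the Protocol 12.1 TEAE definition, including worsening.
4. Define non-TEAE as onset after consent and before first dose, without later worsening. Show these by age group, since they precede any dose.
5. State which 12-<18 column takes an AE arising between the two visits, or one that starts after the first dose and worsens after the second. The SAP has no such rule now.

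The cost is SAP wording and two shells, with no new data. The downside is small columns: one subject moves a rate by 1/12 = 8.3 points to 1/6 = 16.7 points. Print counts and stratum sizes beside every percentage.

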If the starting plasma glucose is <80 mg/dL, no additional insulin will be given. If a plasma glucose level of <80 mg/dL is not achieved within 3 hours of starting the insulin infusion, treatment with study drug should not be given, and the visit should be rescheduled after a minimum 7-day wash-out.

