### 12.3. Reporting Period

For all AEs, the reporting period begins from the time the subject provides informed consent, through the Follow-up Visit. All adverse events will be followed until resolution or the subject is medically stable or the subject exits the study.

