	[PT 2]	xx	x.x	x	x.x	

¹Note: This table presents number and percentage of subjects. A subject is only counted once per PT. A subject may have multiple PTs.

²Any SAE occurred will be summarized in the footnote.

Table 12: Number and percentage of subjects experiencing adverse events by MedDRA® system organ class and preferred term, and treatment dose (continued)

Treatment emergent adverse events (TEAE)						
MedDRA® System Organ Class (SOC)	MedDRA® Preferred Term (PT)	G-Pen™ Dose				
		0.5 mg (N=X)		1.0 mg (N=X)		
		n	%	n	%	
Any SOC	Any PT	xx	x.X	x	x.X	
[SOC 1]	Any PT	xx	x.X	x	x.X	
	[PT 1]	xx	x.X	x	x.X	
	[PT 2]	xx	x.X	x	x.X	
[SOC 2]	Any PT	xx	x.X	x	x.X	
	[PT 1]	xx	x.X	x	x.X	
	[PT 2]	xx	x.X	x	x.X	

¹Note: This table presents number and percentage of subjects. A subject is only counted once per PT. A subject may have multiple PTs.

²Any SAE occurred will be summarized in the footnote.

Table 13: Severity of adverse events and their relatedness to study by MedDRA® system organ class and preferred term, and treatment dose**Non-treatment emergent adverse events (non-TEAE)**

MedDRA® System Organ Class (SOC)	MedDRA® Preferred Term (PT)	G-Pen™ Dose																			
		0.5 mg (N=X)										1.0 mg (N=X)									
		Severity				Relatedness				Severity				Relatedness				Study Drug		Study Device	
		Mild		Moderate		Severe		Study Drug		Study Device		Study Procedure		Mild		Moderate		Severe		Study Drug	
		n	%	n	%	n	%	n	%	n	%	n	%	n	%	n	%	n	%	n	%
Any SOC	Any PT	xx	xx.x	xx	xx.x	xx	xx.x	xx	xx.x	xx	xx.x	xx	xx.x	xx	xx.x	xx	xx.x	xx	xx.x	xx	xx.x
[SOC 1]	Any PT	xx	xx.x	xx	xx.x	xx	xx.x	xx	xx.x	xx	xx.x	xx	xx.x	xx	xx.x	xx	xx.x	xx	xx.x	xx	xx.x
	[PT 1]	xx	xx.x	xx	xx.x	xx	xx.x	xx	xx.x	xx	xx.x	xx	xx.x	xx	xx.x	xx	xx.x	xx	xx.x	xx	xx.x
	[PT 2]	xx	xx.x	xx	xx.x	xx	xx.x	xx	xx.x	xx	xx.x	xx	xx.x	xx	xx.x	xx	xx.x	xx	xx.x	xx	xx.x
[SOC 2]	Any PT	xx	xx.x	xx	xx.x	xx	xx.x	xx	xx.x	xx	xx.x	xx	xx.x	xx	xx.x	xx	xx.x	xx	xx.x	xx	xx.x
	[PT 1]	xx	xx.x	xx	xx.x	xx	xx.x	xx	xx.x	xx	xx.x	xx	xx.x	xx	xx.x	xx	xx.x	xx	xx.x	xx	xx.x
	[PT 2]	xx	xx.x	xx	xx.x	xx	xx.x	xx	xx.x	xx	xx.x	xx	xx.x	xx	xx.x	xx	xx.x	xx	xx.x	xx	xx.x

¹Note: This table presents number and percentage of subjects. A subject is only counted once per PT and is summarized according to their highest severity and closest relationship. A subject may have multiple PTs.

²Any SAE occurred will be summarized in the footnote.

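### Non-TEAEs are defined so that they include every TEAE and are tabulated only by glucagon dose, so events before any glucagon appear under a dose not yet given

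*SAP*

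**What the plan says.** Protocol 12.3 collects AEs early: "the reporting period begins from the time the subject provides informed consent", and it ends with the follow-up contact. Events before the first injection are therefore in the data, including those in children who are never injected.

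SAP 2.5.1 says that all coded AEs are "summarized by system organ class and preferred term, as well as by treatment dose". It describes Tables 12 and 13 in terms of events after dosing, and then adds that "non-TEAE, defined by any AE that occurred after signing informed consent, will be presented in Tables 12 and 13". It defines a TEAE as an AE occurring after G-Pen administration.

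The mock-ups in SAP Appendix I carry this out by dose. Table 12 is titled "Number and percentage of subjects experiencing adverse events by MedDRA® system organ class and preferred term, and treatment dose" and Table 13 "Severity of adverse events and their relatedness to study by MedDRA® system organ class and preferred term, and treatment dose". In each, the non-TEAE panel has two column groups, 0.5 mg (N=X) and 1.0 mg (N=X). There is no column for pre-dose, not dosed or total. The SAP does not define N for these columns or say whether a column means planned, actual, next or last dose. A footnote to both tables says that any SAE will be summarised there. Listings 1 to 3 cover protocol deviations, physical examination findings and pregnancies, and the Appendix II listings cover glucagon.

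Protocol 10.3 puts subjects with at least one dose in the safety analysis, and Protocol 13.3.1 bases the AE percentage on exposed subjects.

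**The concern.** In the period before dosing, glucose is deliberately lowered with insulin. Harm from that procedure before the first injection would be looked for in the non-TEAE panel, and Table 13 has a relatedness column for study procedure. A split of that panel by glucagon dose tells the reader nothing, because no glucagon has been given. It can also mislead, since the table appears to attribute the event to a dose.

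The definition adds a second problem. Read literally, the non-TEAE panel is an all-AE panel, and pre-dose events are not shown separately anywhere.

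Some children may be consented, and possibly induced, without ever being dosed. Protocol 7.2 says that when the glucose target is not reached in 3 hours, "treatment with study drug should not be given, and the visit should be rescheduled". The Table 3 mock-up has rows for termination before the first treatment visit. Nothing in the planned output clearly has a place for a non-serious event in such a child.

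**Working it through.** The plan states no figure on this point, so the check sets the text against the table shells and then counts denominators.

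**1. Do the two categories exclude each other?**
- TEAE: AE after G-Pen administration. Non-TEAE: any AE after consent (both SAP 2.5.1).
- Consent precedes all screening procedures (Protocol 10.1), so every post-dose event is also post-consent. Every TEAE therefore meets the non-TEAE definition.
- Subtracting one panel from the other does not recover the pre-dose events, because each subject counts once per preferred term. As an illustration, one child with the same event before and after dosing gives 1 in the literal non-TEAE panel and 1 in the TEAE panel. The difference is 0, although one child had a pre-dose event.

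**2. Where can a pre-dose event go?**
- Columns mean actual dose: a child dosed later is shown under a dose not yet given when the event occurred. A child never dosed has no column.
- Columns mean planned dose (Protocol 9.1 allocates by age at screening): a child never dosed is shown under a dose never received.
- Neither reading gives a column that describes the child's exposure at the time of the event.

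**3. What are the denominators when everyone is dosed?**

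Ages 2 to under 12 receive 0.5 mg once. Ages 12 to under 18 receive 1.0 mg and then 0.5 mg (Protocol Table 3). With k children dosed per age group and all adolescents completing both visits:
- N(0.5 mg) = 3k
- N(1.0 mg) = k
- unique children = 3k

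SAP 1.3 (k = 12): N(0.5 mg) = 36, N(1.0 mg) = 12, 36 unique children. One adolescent event before Visit 1 reads 1/12 = 8.3% under 1.0 mg, 1/36 = 2.8% under 0.5 mg, or both.

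Protocol synopsis (k = 8): N(0.5 mg) = 24, N(1.0 mg) = 8, 24 unique children. The same event reads 1/8 = 12.5% or 1/24 = 4.2%.

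The column Ns sum to 4k, so every adolescent is in the base twice.

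**4. How many consented children could lack an actual-dose column?**
- Both documents anticipate about 48 screened.
- Protocol synopsis: 48 − 24 = 24 (24/48 = 50%).
- SAP 1.3: 48 − 36 = 12 (12/48 = 25%).
- This is screened minus treated, so it would include screen failures, who never reach insulin induction. The gap between 12 and 24 only reflects the two documents' different numbers treated. Neither document gives a rate of failed induction or of dropout between consent and dosing.

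**The case against.** The strongest reply is that leaving out never-dosed children is a declared choice. Protocol 10.3 and 13.3.1 base safety on exposed subjects, and a consented-subject denominator departs from that. This stands as a reason to state and footnote any second denominator. It does not explain why pre-dose events in children who are later dosed should be split by dose.

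A reader might infer that events in undosed children are counted nowhere. The documents do not support that as a fact. N and the column rule are undefined, and under planned-dose columns such a child would be counted, though under a dose never received. SAEs have the table footnote, and SAP 3.4 has safety results listed for regular sponsor review. A failed induction is rescheduled, so a child dosed later enters the exposed set. The gap is confined to non-serious events in children never dosed, under the actual-dose reading.

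A reader might also take 25 to 50% of children as the share affected. That range is screened minus treated and does not measure children given insulin but no glucagon.

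Two further replies have some force:
- The adolescent sequence is fixed at 1.0 mg then 0.5 mg, so next dose is a natural convention for an event before Visit 1, and nothing says it will be counted twice. But the SAP does not state that convention, and adopting it would still label the event with a dose not yet given.
- The study-procedure column in Table 13 gives procedure-related events in dosed children a labelled place. That place still sits inside a dose column.

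**Conclusion.** The point holds in a limited form. Two defects follow directly from SAP 2.5.1 and the shells, whatever the column rule: the non-TEAE definition contains every TEAE, and a pre-dose event can be shown only under a dose not given when it occurred. For ages 12 to under 18 the column is undefined, and the choice changes the displayed percentage threefold (k against 3k, for example 8.3% against 2.8%), assuming full dosing and both visits completed.

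A third defect is conditional. If columns mean actual dose, a non-serious AE in a never-dosed child has no planned table or listing. The number of such children is unknown, and 12 to 24 of 48 is no more than an upper bound.

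No efficacy result is affected. The change should be made because the planned safety output cannot be produced unambiguously as written, and the repair is small.

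**What to change.** 1. Define non-TEAE in SAP 2.5.1 as onset after consent and before the first G-Pen dose. Say how an event that starts before dosing and worsens afterwards is classed, since Protocol 12.1 treats it as treatment-emergent and the SAP definition does not mention it. Align the sentences describing Tables 12 and 13, which otherwise speak only of post-dose events.
2. In the non-TEAE panels of Tables 12 and 13, replace the dose columns with the three age groups plus total. This also serves the objective of safety for each age group (Protocol 5.2). State N as consented or enrolled subjects, with a footnote that it differs from the exposed set in Protocol 10.3 and 13.3.1.
3. Separate events before and after the start of insulin induction where recorded onset times allow. The documents do not say that the CRF times AE onset this finely, so check that first.
4. Keep dose columns for TEAEs only, with a stated attribution rule for ages 12 to under 18. The rule must cover events during the Visit 2 induction, which follow the 1.0 mg dose and precede the 0.5 mg dose.
5. Add one AE listing that includes never-dosed subjects.

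The cost is one definition, two table shells, one listing and a footnote. The downside is a second denominator that readers must keep apart from the exposed-subject N. No added data collection is needed, except that the induction split in step 3 depends on the onset times available.
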